13.1.1.2. Subject Global Aesthetic Improvement Scale (S-GAIS)

Subjects in the observation-only group will complete the S-GAIS as described below at the final study visit (month 12 or early termination) using the pre-treatment Day 1 image (Baseline) of the assigned quadrant in the double-blind study for comparison.

For subjects who elected to receive EN3835 treatment, the S-GAIS assessment will be done on Day 71 of the treatment course and then at month 12 or the final study visit and compared back to the pre-dosing Screening B image (Baseline for treatment subjects) of the selected quadrant. All treated subjects will be instructed to answer the following question: *How would you rate the appearance of your treated cellulite after treatment?*

The S-GAIS assessment will occur after the subject has completed the PR-PCSS assessment to avoid introducing potential bias to the static PR-PCSS assessment. Each subject will view the pre-dosing Screening B visit digital image alongside their Day 71 treatment course visit and month 12 or end of study visit digital image of their selected quadrant to aid in the assessment (Table 6). Subjects will circle the rating below that best represents their answer.

Table 6: Subject Global Aesthetic Improvement Scale (S-GAIS)

Rating	Response Option	Description
+3	Very much improved	My treated cellulite looks very much better.
+2	Much improved	My treated cellulite looks much better, but additional treatment would slightly improve the result.
+1	Improved	My treated cellulite looks better, but additional treatment is necessary.
0	No change	My treated cellulite looks essentially the same as it did originally.
-1	Worse	My treated cellulite looks worse than it did originally.
-2	Much worse	My treated cellulite looks much worse than it did originally.
-3	Very much worse	My treated cellulite looks very much worse than it originally.

13.1.1.3. Subject Satisfaction with Cellulite Treatment Assessment

For observation-only subjects (not receiving EN3835) the subjects will assess their satisfaction with cellulite treatment at the 12 month or end of study visit by being instructed to answer the following question: *Today, how satisfied are you with the results of the cellulite treatment you received on the specific area or areas on your buttocks or thighs that were treated?* Subjects will circle the rating in the below table that best represents their answer.

For subjects who have elected to receive EN3835 either through re-treatment or re-dosing, the subject satisfaction with the cellulite treatment (Table 7) will be done at the treatment course Day 71 and the month 12 visit or end of study visit. Subjects will be instructed to answer the following question: *Today, how satisfied are you with the results of the cellulite treatment you received on the specific area or areas on your buttocks or thighs that were treated?* Subjects will circle the rating below that best represents their answer.

Table 7: Subject Satisfaction with Cellulite Treatment Assessment

Rating	Description
+2	I am very satisfied with the cellulite treatment on my buttocks or thighs.
+1	I am satisfied with the cellulite treatment on my buttocks or thighs.
0	I am neither dissatisfied nor satisfied with the cellulite treatment on my buttocks or thighs.
-1	I am dissatisfied with the cellulite treatment on my buttocks or thighs.
-2	I am very dissatisfied with the cellulite treatment on my buttocks or thighs.

13.1.1.4. Clinician-Reported Photonicumeric Cellulite Severity Scale (CR-PCSS)

The CR-PCSS will be conducted for the purpose of assessing the severity of cellulite in the buttock or thigh; there are separate scales for buttocks or thighs. The scales are 5-level photonicumeric scales developed specifically for clinicians and used by the investigator to assess the severity of the subject's cellulite in the quadrants by live assessments of the subject's quadrant(s); the ratings range from 0 (None) to 4 (Severe) with labels and descriptors to aid the investigator in the assessments.

Investigators will have been trained on the use of the CR-PCSS. For observation-only subjects, the CR-PCSS will be done at 3, 6, 9, and 12 months or at the end of study visit.

For subjects who elected to receive EN3835 after the study drug blind is broken in study EN3835-201 as a re-treatment or re-dosing, the Investigator, at the Screening B visit (Baseline) will determine severity of cellulite of the 4 quadrants by assessing live subjects using the CR-PCSS for buttock ([Figure 3](#)) and thighs ([Figure 4](#)) after the subject has completed their self-assessment using the PR-PCSS. The eligible quadrant chosen for injection will be at the discretion of the subject. Before injections on treatment visit Days 22 and 43 and on visit Day 71; Investigators will evaluate the selected quadrant by live assessments. If the buttock is the treated region, the Investigator will use the CR-PCSS for the buttock to make his/her evaluation; if the thigh is the treated region, the Investigator will use the CR-PCSS for the thigh to make his/her evaluation. In each case, the Investigator will make his/her assessment independently and after the subject has conducted their self-assessment using the PR-PCSS.

Figure 3: Clinician-Reported Photonumeric Cellulite Severity Scale (CR-PCSS) for the Buttock

Clinician Reported Photonumeric Cellulite Severity Scale (CR-PCSS) – Buttock

0 None

No dimples or evident cellulite

1 Almost None

Few dimples that are mostly superficial in depth

2 Mild

Several dimples of which most are shallow in depth

3 Moderate

Many dimples of which most are moderate in depth

4 Severe

A lot of dimples with some of more severe depth

Produced by CANFIELD Scientific, Inc.

Version 10.0

© 2015 Endo Pharmaceuticals
Confidential – Not to be distributed

Figure 4: Clinician-Reported Photonumeric Cellulite Severity Scale (CR-PCSS) for the Thigh

Clinician Reported Photonumeric Cellulite Severity Scale (CR-PCSS) – Thigh

0 None

No depressions or raised areas

1 Almost None

A few depressions or undulations that are mostly superficial in depth

2 Mild

Several undulations that are shallow in depth with areas of slight protuberances

3 Moderate

Many undulations with alternating areas of protuberances and depressions, of which most are moderate in depth

4 Severe

A lot of undulations with alternating areas of protuberances and depressions, some of more severe depth

Produced by CANFIELD Scientific, Inc.

Version 10.0

© 2015 Endo Pharmaceuticals
Confidential – Not to be distributed

13.1.1.5. Investigator Global Aesthetic Improvement Scale (I-GAIS)

Investigators will complete the I-GAIS on subjects in the observation-only group as described below at the final study visit (month 12 or early termination) and a comparison back to the pre-treatment Day 1 (Baseline) image of the assigned quadrant of the double-blind study.

On Day 71 of the treatment course and the 12 month or end of study visit, the Investigator will determine the degree of improvement from the Screening B digital image of the selected quadrant by comparing the cellulite in live assessment on Day 71 and at month 12 or study end to the Screening B pre-treatment (Baseline) image of the subject's selected quadrant (Table 8). The I-GAIS assessment will occur after the CR-PCSS assessment (section 13.1.1.4) to avoid introducing potential bias to the static CR-PCSS assessment by the Investigator at the site. The Investigator will circle the rating below that best represents their answer.

Table 8: Investigator Global Aesthetic Improvement Scale (I-GAIS)

Rating	Response Option	Description
+3	Very much improved	Optimal cosmetic result from treatment of the treated dimples
+2	Much improved	Marked improvement in the treated area appearance from before treatment, but not completely optimal
+1	Improved	Obvious improvement in the treated area appearance from before treatment, but additional treatment is indicated
0	No change	The treated area appearance is essentially the same as before treatment
-1	Worse	The treated area appearance is worse than before treatment
-2	Much worse	Marked worsening in appearance from the initial condition
-3	Very much worse	Obvious worsening in appearance from the initial condition

13.1.1.6. Hexsel Cellulite Severity Scale

The Hexsel Cellulite Severity Scale (referred to as the Hexsel CSS) is a photonumeric scale that looks at 5 key morphologic features of cellulite: (A) number of evident depressions, (B) depth of depressions, (C) morphological appearance of skin surface alterations, (D) laxity, flaccidity or sagging of skin, and (E) current classification scale based on medical literature including Nürnberg and Müller.(12,13) Each of these features is evaluated on a 4-point scale from a low of 0 to a high of 3 as described in Table 9 (see Appendix B). The total score is the summation of all 5 features.

For subjects in the observation-only group, the Hexsel CSS will be done at the month 12 or the end of study visit.

For the subjects electing treatment (re-treatment or re-dosing) with EN3835 the Investigator or qualified designee will independently use the Hexsel CSS to assess the severity of EFP in all quadrants at Screening B visit and the selected quadrant on Day 71 of the course of treatment and at month 12 or end of study visit. All cellulite assessments should be made while the subject is in the standing position with relaxed gluteus muscles. However, when evaluating the subject for Category E (classification scale by Nürnberg and Müller) (13) if the subject has no evident depressions, the subject should be asked to contract her gluteus muscles or the pinch test should

be applied (by pinching the skin between the thumb and index finger) so the Investigator or qualified designee can differentiate between scores/grades of zero (0) or I.

Table 9: Hexsel Cellulite Severity Scale

A	Number of evident depressions	0=none/no depressions 1=a small amount: 1-4 depressions are visible 2=a moderate amount: 5-9 depressions are visible 3=a large amount: 10 or more depressions are visible
B	Depth of depressions	0=no depressions 1=superficial depressions 2=medium depth depressions 3=deep depressions
C	Morphological appearance of skin surface alterations	0=no raised areas 1='orange peel' appearance 2='cottage cheese' appearance 3='mattress' appearance
D	Grade of laxity, flaccidity, or sagging skin	0=absence of laxity, flaccidity, or sagging skin 1=slight draped appearance 2=moderate draped appearance 3=severe draped appearance
E	Classification scale by Nürnberger and Müller ^a	0 = zero grade = Grade or Stage 0 = There is no alteration of the skin surface. 1 = first grade = Grade or Stage I = The skin of the affected area is smooth while the subject is standing or lying, but the alterations to the skin surface can be seen by pinching the skin or with muscle contraction. 2= second grade = Grade or Stage II = The orange skin or mattress appearance is evident when standing, without the use of any manipulation (skin pinching or muscle contraction). 3= third grade = Grade or Stage III = The alterations described in Grade or Stage II, are present together with raised areas and nodules.

Source: Hexsel DM, Dal’Forno T, Hexsel CL. A validated photonumeric cellulite severity scale. *J Eur Acad Dermatol Venereol.* 2009;23(5):523-528.

^a Subjects should be evaluated in the standing position with relaxed gluteus muscles. However, if the subject has no evident depressions, they should be asked to contract their gluteus muscles or the pinch test should be applied (by pinching the skin between the thumb and index finger) in order to differentiate between grade/stage of zero (0) or I.

14. ASSESSMENT OF SAFETY

14.1. Definitions

14.1.1. Adverse Event

An adverse event (AE) is any unfavorable or unintended change in body structure (signs), body function (symptoms), laboratory result (eg, chemistry, ECG, X-ray, etc), or worsening of a pre-existing condition associated temporally with the use of the study medication whether or not considered related to the study medication. AEs will be captured once a subject has signed the informed consent. AEs include:

- Changes in the general condition of the subject
- Subjective symptoms offered by or elicited from the subject
- Objective signs observed by the Investigator or other study personnel
- All concurrent diseases that occur after the start of the study, including any change in severity or frequency of pre-existing disease
- All clinically relevant laboratory abnormalities or physical findings that occur during the study

A treatment-emergent adverse event (TEAE) is any condition that was not present prior to treatment with study medication but appeared following treatment, was present at treatment initiation but worsened during treatment, or was present at treatment initiation but resolved and then reappeared while the individual was on treatment (regardless of the intensity of the AE when the treatment was initiated).

All AEs, including both observed or volunteered problems, complaints, signs or symptoms must be recorded on the AE page of the eCRF, regardless of whether associated with the use of study medication. This would include AEs resulting from concurrent illness, reactions to concurrent medication use, or progression of disease states (excluding the disease under study). A condition present at baseline that worsens after initiation of study treatment will be captured as an AE; the onset date will be the date the event worsened. The AE should be recorded in standard medical terminology when possible.

14.1.2. Serious Adverse Event

A serious adverse event (SAE) is defined as an AE that:

- Results in death
- Is immediately life-threatening (there is an immediate risk of death from the AE as it occurred; this does not include an AE that had it occurred in a more serious form may have caused death)
- Results in or prolongs an inpatient hospitalization (Note: a hospitalization for elective or pre-planned surgery, procedure, or drug therapy does not constitute an SAE)

- Results in permanent or substantial disability (permanent or substantial disruption of one's ability to conduct normal life functions)
- Is a congenital anomaly/birth defect (in offspring of a subject using the study medication regardless of time to diagnosis)
- Is considered an important medical event

Important medical events are defined as events that, based upon appropriate medical judgment, may jeopardize the subject and may require medical or surgical intervention to prevent one of the other serious outcomes. Examples of important medical events include allergic bronchospasm requiring intensive treatment in an emergency room or at home, blood dyscrasias or convulsions that do not result in inpatient hospitalization, or the development of drug dependency or drug abuse.

14.2. Monitoring Adverse Events

At each visit, subjects will be queried regarding any AEs that have occurred since the last visit. Subjects will be asked to volunteer information concerning AEs with a non-leading question such as, "How do you feel?" Study site personnel will then record all pertinent information in the source documents and the eCRF. The study drug compliance record should also be reviewed to detect potential overdoses (intentional/unintentional).

14.3. Relationship to Study Drug

The degree of "relatedness" of the AE to the study medication must be described using the following scale:

- **Not related** indicates that the AE is definitely not related to the study medication.
- **Unlikely related** indicates that there are other, more likely causes and study medication is not suspected as a cause.
- **Possibly related** indicates that a direct cause and effect relationship between study medication and the AE has not been demonstrated, but there is evidence to suggest there is a reasonable possibility that the event was caused by the study medication.
- **Probably related** indicates that there is evidence suggesting a direct cause and effect relationship between the AE and the study medication.

It is the Sponsor's policy to consider "Probably related" and "Possibly related" causality assessments as positive causality. "Not related" and "Unlikely related" causality assessments are considered as negative causality.

Assessments will be recorded on the eCRF and must indicate clearly the relationship being assessed. For example, an AE that appears during a placebo run-in phase would be assessed with respect to the placebo treatment received and/or study procedures conducted during this phase. If the AE continued into an active treatment phase, the relationship would be assessed for the active treatment phase only if the AE worsened.

14.4. Intensity Assessment

The intensity (or severity) of AEs is characterized as mild, moderate, or severe:

- **Mild** AEs are usually transient, requiring no special treatment, and do not interfere with the subject's daily activities.
- **Moderate** AEs introduce a low level of inconvenience or concern to the subject and may interfere with daily activities, but are usually ameliorated by simple therapeutic measures.
- **Severe** AEs interrupt a subject's usual daily activity and typically require systemic drug therapy or other treatment.

When the intensity category of an AE changes, the greatest intensity during that continuous episode should be recorded.

14.5. Reporting Adverse Events and Serious Adverse Events

14.5.1. Reporting Adverse Events

Throughout the study, AEs will be documented on the source document and on the appropriate page of the eCRF whether or not considered treatment-related. This includes any new signs, symptoms, injury or illness, including increased severity of previously existing signs, symptoms, injury, or illness. Conditions existing prior to screening will be recorded as part of the subject's medical history. The Investigator is responsible for assessing the relationship of AEs to the study medication; relationship will be classified as not related, unlikely related, possibly related, or probably related.

All AEs will be collected by the Investigator from the time of signing the informed consent through 30 days after the last dose of study medication; this includes any AEs that are ongoing at the time of completion/termination of the study. All ongoing AEs must be followed until resolution or for 30 days after the subject's last study visit, whichever comes first.

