9. OBJECTIVES

9.1. Primary Objective

The primary objective of this study is to assess long-term safety of EN3835 0.84 mg at scheduled intervals over 1 year (12 months) in all subjects with EFP who elect to enroll in this open-label trial regardless of their decision to receive treatment (re-treatment or re-dosing) of open-label EN3835 or opt to receive no treatment.

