Selection of dimples to be treated in the selected quadrant is at the discretion of the Investigator or qualified designee. Dimples must be well-defined and evident when the subject is standing in a consistent relaxed pose (without the use of any manipulation such as skin pinching or muscle contraction). Each subject will receive 3 treatment sessions of study drug in the selected quadrant. During each treatment session, the treatment quadrant will be photographed before and after dimple marking while the subject is standing in a consistent relaxed pose as described in the Photography Manual. The cellulite severity assessments using the PR-PCSS and CR-PCSS will be completed prior to dimple marking at treatment visits 2, 3, and 4/end of treatment.

12.1.4.1. Screening B (Days -14 to -1 Relative to Open-Label Treatment Visit Day 1)

Subjects meeting the relevant criteria listed in section 11.2 may be eligible for treatment in the open-label study. The following procedures will be performed and documented during the screening period:

1. Evaluate eligibility based on inclusion/exclusion criteria (section 11.2)
2. Subject will have digital photographs taken of the 4 targeted quadrants of the study (left and right buttocks, and left and right posterolateral thighs) (section 13.1)
3. Subjects will get instruction on the use of the PR-PCSS (Appendix D)
4. Subjects will rate each quadrant using the PR-PCSS while viewing their digital images (section 13.1.1.1)
5. The Investigator will conduct independent live assessments of subject's cellulite severity of each quadrant using the CR-PCSS (section 13.1.1.4) after the subject completes her rating and with no knowledge of the subject's ratings of her quadrants.
6. The Investigator will conduct live cellulite evaluation of each quadrant using the Hexsel CSS (section 13.1.1.6).

7. If at least 1 quadrant qualifies based on PR-PCSS, CR-PCSS, and Hexsel CSS ratings, subject may return for treatment on treatment visit 1. If none of the 4 quadrants qualify, the subject may remain in the study and have safety and cellulite severity evaluations performed at 3-month intervals but is not eligible for treatment.
8. Subject will select an eligible quadrant (based on qualifying scores) to be treated at their discretion.
9. Medical history including EFP history. Medical history will be based on EN3835-201 eCRF; only updates to the history need to be captured at Screening B visit.

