1.2. Schedule of Study Assessments

[Table 2](#) lists the schedule of observation assessments, [Table 3](#) lists the schedule of treatment session assessments, [Table 4](#) lists the schedule of long-term durability assessments.

The schedule of observation assessments is applicable for both observation only and treated subjects in current study. For example, if subjects received treatments (ie, re-treatment, re-dosing, or a first treatment) in current study may be scheduled for observation assessments up to maximum of 1 year for each treated quadrant.

NOTE: Observation visits ([Table 2](#)) in the open-label extension study begin after completion of double-blind study (Day 71). Treatment sessions ([Table 3](#)), if elected, will begin after study drug blind is broken in study EN3835-201 while observation visits continue concurrently. Durability visits ([Table 4](#)) are for the subjects who received active treatment in EN3835-201 and scored an improvement of at least 1 level on both the CR-PCSS and the PR-PCSS at the same visit on or before Day 71 in the double-blind study EN3835-201.

Table 2: Schedule of Observation Assessments

Procedures	Screening A ^a (≥Day 71 Visit of Double-blind Study)	Visit 1 Day 90 ^b (±7 days)	Visit 2 Day 180 ^b (±7 days)	Visit 3 Day 270 ^b (±7 days)	Visit 4 End of Study/ Early Termination Day 360 ^{b,f} (±7 days)
Informed Consent	X				
Inclusion/Exclusion	X				
Digital photography		X ^c	X ^c	X ^c	X ^c
Prior/Concomitant Medications/Procedures	X	X	X	X	X
Body weight		X	X	X	X
Vital signs		X	X	X	X
Collection of samples:					
• Clinical laboratory					X
• Anti-AUX-I/anti-AUX-II antibody level					X
Subject cellulite assessments:					
• Patient Reported Photonumeric Cellulite Severity Scale (PR-PCSS)		X ^{d,e}	X ^{d,e}	X ^{d,e}	X ^{d,e}
• Subject Global Aesthetic Improvement (S-GAIS)					X ^{d,e}
• Subject satisfaction with cellulite treatment assessment					X ^{d,e}
Investigator cellulite assessments:					
• Clinician Reported Photonumeric Cellulite Severity Scale (CR-PCSS)		X ^e	X ^e	X ^e	X ^e
• Hexsel Cellulite Severity Scale (CSS)					X ^e
• Investigator Global Aesthetic Improvement (I-GAIS)					X ^e
Injection site reactions/local tolerability in assigned quadrant from EN3835-201 study		X	X	X	X
Adverse events		Monitored Throughout Study			

^a Informed consent for open-label observation assessments and optional treatment election.

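### Section 14.5.1 makes an unchanged, non-serious reaction ongoing from EN3835-201 medical history rather than a 202 adverse event, and no analysis of the first-course quadrant is specified

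*Combined protocol and SAP*

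**What the plan says.** Protocol 14.5.1 (Amendment 2 text; the sentence is the same in Amendment 1 and in the original protocol) gives the rule: "Conditions existing prior to screening will be recorded as part of the subject's medical history". The same paragraph says what is documented as an adverse event: "This includes any new signs, symptoms, injury or illness, including increased severity of previously existing signs, symptoms, injury, or illness". Events that do qualify have a follow-up rule: "All ongoing AEs must be followed until resolution or for 30 days after the subject's last study visit, whichever comes first". Section 14.1.1 sets the start of capture: "AEs will be captured once a subject has signed the informed consent".

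The 202 study has two screenings. Screening A follows the Day 71 assessments of EN3835-201 (Sections 10.1 and 12.1.1; SAP Table 2). Screening B follows the breaking of the 201 blind and applies to women who want treatment in 202 (Sections 10.1 and 12.1.4.1). At Screening B the history is not taken afresh: "Medical history will be based on EN3835-201 eCRF; only updates to the history need to be captured at Screening B visit".

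The primary objective in Section 9.1 is 12-month safety in all enrolled women, "regardless of their decision to receive treatment (re-treatment or re-dosing) of open-label EN3835 or opt to receive no treatment". Section 17.2.2 accordingly puts women dosed only in 201 into the protocol's Safety population.

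SAP Table 2 schedules, at Days 90, 180, 270 and 360, "Injection site reactions/local tolerability in assigned quadrant from EN3835-201 study". The endpoint listed in Protocol 17.6 and SAP 7 is local tolerability in the selected quadrant. Protocol Section 7 defines 'assigned quadrant' (201) and 'selected quadrant' (202) as separate terms.

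SAP 7.4 requires a treatment-emergent event to start on or after a 202 treatment start. It makes treatment-related events a subset of those and summarises duration for treatment-related events. Observation-phase events are tabulated from Screening A (SAP 2), with no rule for events already open on that date.

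**The concern.** A rule that treats pre-screening conditions as history suits a trial in which screening precedes first exposure. Here screening comes after up to three sessions of the drug whose long-term safety is being studied. What the rule sets aside can therefore include reactions to that drug.

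These are also the reactions a 12-month extension should describe best. A local reaction still present at entry has outlasted the durations that the protocol's background reports. For women who take no further treatment, the persistence of first-course reactions is a large part of what long-term safety means. At stake is whether the 202 report can say how many women entered with an open reaction, how long it lasted and whether it resolved.

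**Working it through.** The documents give no figure on this point to reproduce. The check is mainly textual, followed by timing and a bounding calculation.

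**1. Where each kind of event goes.** Take an event that began after EN3835 in 201 and is ongoing at Screening A.

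| State of the event | 202 adverse event under 14.5.1? | Treatment-emergent under SAP 7.4? | Other route |
|---|---|---|---|
| Unchanged, non-serious, local | No: neither new nor worse | No: onset precedes any 202 dose | Observed under SAP Table 2; no analysis named for the assigned quadrant |
| Unchanged, non-serious, not local | No | No | None in the text shown |
| Worsened | Yes, dated from the worsening (14.1.1) | Only if it worsens on or after a 202 treatment start | Otherwise observation-phase tables |
| Serious and judged related | Reportable at any time after dosing (14.5.2) | No, on onset date | Expedited report |

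The first two rows are the gap. Amending 14.5.1 alone would not close it. The duration summary is restricted to treatment-related events, which must be treatment-emergent, so a 201-onset event cannot enter it even if it is recorded on a 202 page. For a woman re-treated in the same quadrant, assigned and selected quadrant coincide and the named endpoint covers it from then on. For observation-only and re-dosed women it does not cover the 201 quadrant.

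**2. Medical history as a fallback.** It is not a Screening A procedure in SAP Table 2. It is taken at Screening B, and updates are taken at the Day 450 durability visit (SAP Table 4). A woman who declines treatment has no scheduled history collection at entry.

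**3. Timing.** Assume 201 used the 202 session days (1, 22, 43). Section 8.3.1.4 says only that there are up to three sessions about 21 days apart, with the last visit on Day 71.

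- Day 71 − Day 43 = 28 days from the last session to the earliest entry.
- Background: pilot, mean 18 days to resolution (8.3.1.1); Phase 1b, resolved within 3 weeks, 21 days (8.3.1.2); Phase 2a, most events resolved before the next session (8.3.1.3).

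A reaction that is open at entry has therefore lasted at least 28 days, longer than these figures.

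**4. Size.** Section 17.1: 0.95 × 350 = 332.5, the planned 333. With 1:1 allocation and equal rollover by arm (an assumption), 0.95 × 175 = 166 women had EN3835 in 201.

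- If the Phase 1b 3-week limit holds: none open at 28 days, so about 0.
- If durations have the pilot's mean of 18 days and every woman reacted at session 3: exponential, exp(−28/18) = 0.211, and 166 × 0.211 = 35. Lognormal with coefficient of variation 0.5, 0.75 or 1.0: 0.121, 0.160 or 0.172; the lowest gives 166 × 0.121 = 20.
- Entry at the late edge of Day 71, using 202 windows: (71 + 5) − (43 − 3) = 36 days. Shares fall to 0.044–0.106 (lognormal) and 0.135 (exponential).
- Entry at the end of the Day 90 window: 97 − 43 = 54 days; exp(−54/18) = 0.050, about 8 women.

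The range runs from 0 to about 35, and the documents do not locate the true value within it.

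**5. A separate limit.** Section 14.5.1 collects events "from the time of signing the informed consent through 30 days after the last dose of study medication". With no 202 dose, that is 43 + 30 = Day 73, which is 90 − 73 = 17 days before the first observation visit. This does not come from the history rule and is not counted here.

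**The case against.** The strongest reply is that the plan is unclear rather than shown to lose data.

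- *'Screening' is not specified.* True. History at Screening B is built from the 201 case report form, which would also fit a reading in which history means conditions before 201. But the only screenings this protocol defines follow 201 dosing, and nothing in 14.5.1 points back to the 201 screening. If the word is ambiguous, sites may code the same reaction differently, which also calls for a rule.
- *Local reactions are still observed.* This stands. SAP Table 2 looks at the 201 quadrant at four visits, so the observations are not lost. What is missing is a stated analysis of them, and the row does not reach non-local events.
- *Worsened reactions and related serious events are captured.* This stands, and it confines the point to unchanged, non-serious events.
- *The event belongs to the 201 record.* Quite possibly its onset, severity and relationship are there. The 201 rules for ongoing events are not in the documents, so neither loss of the event nor continued follow-up can be shown. What is at risk is persistence and resolution after rollover.
- *The text may not be current.* The 14.5.1 wording is from Amendment 2, whose own Table 2 is not in the part shown. The SAP's visits at Days 450 to 720 do not appear in the protocol text shown, which suggests a later amendment. This should be checked before any change is drafted.

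**Conclusion.** The point holds in a limited form. Read literally, an unchanged, non-serious reaction that began after EN3835 in 201 and is ongoing at rollover is not a 202 adverse event, cannot be treatment-emergent, and is absent from the SAP's adverse-event and duration summaries. The assigned-quadrant observations that could partly make up for this have no specified analysis. This rests on reading 'screening' as a 202 screening and on 14.5.1 being current.

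A reader might infer two stronger things. One is that any reaction from 201 drops out of the long-term safety data. The documents do not support this: worsening is an adverse event, related serious events are always reportable, and local reactions remain under scheduled observation. The other is that first-course harm is understated by some 20 to 35 women. That count takes its mean from a pilot of 10 women given 0.58 mg by template, adds an assumed distribution, and supposes that every woman reacted at session 3. The Phase 1b statement would give about zero. The number affected is unknown, and understatement of harm is not demonstrated.

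I would call this a cheap improvement. Its merit does not depend on the count, because whatever persistent reactions exist are the ones that the rule sets aside.

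**What to change.** 1. **Protocol 14.5.1:** limit the medical-history rule to conditions that began before the first study-drug dose in EN3835-201.
2. **Protocol 14.5.1 and eCRF:** carry any 201 adverse event open at Screening A into the 202 record with its 201 onset date, severity and relationship, and follow it to resolution or last contact. Carry full onset dates, because SAP 7.4 assigns events whose timing cannot be determined to treatment course 1.
3. **SAP 7.4:** add an 'ongoing from EN3835-201' row to the observation-phase table, by 201 arm, with duration counted from the 201 onset. Keep it apart from new-onset events so that nothing is counted twice across the two studies.
4. **SAP 7:** name local tolerability in the assigned quadrant as an endpoint and summarise the Day 90 to Day 360 observations.

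The cost is protocol wording, an eCRF carry-over of open 201 events (subject numbers already carry over under Section 12.1.3), one or two extra table rows and slightly higher adverse-event counts.
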